8.2.2 Secondary Endpoints

1. Statistically non-inferior image quality scores for the self-gated MUSIC-MRI in each of the 7 important anatomical structures compared with the ventilator-gated MUSIC-MRI.
2. Statistically non-inferior sharpness measurements at the ascending aorta and the interventricular septum using the self-gated MUSIC-MRI compared with the ventilator-gated MUSIC-MRI.
3. A statistically non-inferior blood-myocardium CNR measurements.

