18.3 Definition of Numeric Efficacy Outcomes

Subjective Image Quality Scores: The image quality will be independently scored by 2 board certified blinded readers with >5 years of cardiovascular MRI reading experience using a 1-4 point scale (1). The composite image quality score for each subject will be a number between 7 (all subjective image quality scores are 1=non-diagnostic) to 28 (all subjective image quality scores are 4=clear visualization). The scores will be assessed separately for each of the following seven anatomical structures that are important for imaging pediatric CHD patients: the aortic root, the pulmonary artery (PA), the coronary arteries, the out-flow tracts, the valves, the ventricles, and the atria. If the difference in the composite score is greater than or equal to 4 between two image readers, the readers will read the image together in a consensus reading session and arrive at a consensus for each of the 7 structures. The criteria for assigning scores will be as follows: 1) For **aortic root and PA**, 1=nondiagnostic (vessels not visualized or diagnostically not assessable due to small size and /or motion artifact and /or poor contrast enhancement), 2=vessels visualized but with poor contrast enhancement and /or motion artifact so as to limit confident assessment and measurement of dimensions, 3=vessels visualized with good contrast so as to enable confident assessment of patency but with poor edge definition due to motion artifact so as to limit confident measurement of dimensions, 4=vessels visualized with good contrast and good edge definition such that patency and dimensions are confidently assessable; 2) For **coronary arteries**: 1=nondiagnostic (vessels not visualized or diagnostically not assessable due to small size and /or motion artifact and /or poor contrast enhancement), 2=only origins of main coronary arteries confidently identifiable, 3=origins and proximal course of RCA and left anterior descending (LAD) confidently evaluable, 4=origin, proximal and mid courses of RCA and LAD and proximal takeoff of left circumflex confidently evaluable; 3) For **out-flow tracts and valves**: 1=nondiagnostic (structures not visualized or diagnostically not assessable due to small size and /or motion artifact and /or poor contrast enhancement, 2=annulus and sinotubular junction visualized but borders not sufficiently well defined for confident measurement, 3=annulus and sinotubular junction visualized with well defined borders sufficient for confident measurement, 4=annulus and sinotubular junction clearly visualized with well defined borders sufficient for confident measurement and valve leaflets clearly seen; 4) For the **ventricles and atria**: 1=nondiagnostic (chambers not visualized or diagnostically not assessable due to small size and /or motion artifact and /or poor contrast enhancement, 2=chambers distinguishable but walls poorly defined and only gross features evaluable, 3=chambers clearly distinguishable with well defined septum and free walls confidently evaluable but with poor definition of the papillary

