18.4 Primary Efficacy Endpoints

18.4.1 Part I – Difference in the composite image quality score between Feraheme and Ablavar

The primary efficacy endpoint for Part I is the composite image quality score, which is defined as the sum of the subject image quality scores assigned to seven important anatomical structures for pediatric CHD patients: the aortic root, the PA, the coronary arteries, the outflow tracts, the valves, the ventricles, and the atria. The score will be the average scores from all the image readers. The consensus reading will occur if the difference in the composite score from the same image is 4 or greater. The composite image quality score will be tested for normality using the Shapiro-Wilk and Shapiro-Francia tests. For normally distributed data, comparison will be made between the composite image quality scores for Feraheme and Ablavar using a parametric two-sided t-test with an appropriate transformation if needed. If statistical transformation of the image quality score is not possible, a non-parametric Wilcoxon-rank-sum test can be considered. The null hypothesis is that there is no difference in the composite subjective image quality scores between Feraheme and Ablavar. This comparison will be a two-sided test at the overall 0.05 level of significance. Summary statistics of mean, standard deviation and their 95% confidence intervals of each contrast agent and the difference will be used for statistical description. There will be a formal interim analysis and a primary analysis for image quality score. The primary analysis of image quality scores will be performed when 80 CHD subjects are enrolled and the images are scored by the image readers. Scores for subjective image quality, sharpness and CNR measurements will remain blinded from the Investigators and only the study statistician will be able to pair the contrast assignment and the score.

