[Interim Analyses]: To avoid performing a study with larger-than-necessary enrollment for Part I of our study, a formal interim analysis for the composite imaging score will be performed at approximately 20 CHD subjects for each of the contrast group (50% of the target number for the primary analysis). Alpha-spending for the interim analyses and the primary analysis will be 0.025 and 0.025 (both two-sided), respectively. The overall alpha for the composite image quality score will be preserved at the two-sided 0.05 significance level. The interim analysis of the composite image quality score will be conducted by an independent statistician under the charter of the DMC.

The interim effect of Feraheme compared to the Ablavar of ventilator-gated MUSIC-MRI based on the average composite score from two image readers will be tested with a two group t-test with an appropriate transformation if needed. Non-parametric Wilcoxon rank sum test will be considered if the data are not normally distributed based on the Shapiro-Wilk and Shapiro-Francia tests and transformation is not feasible.

18.4.2 Part II – Difference in the composite image quality score between ventilator-gated and self-gated MUSIC-MRI

The primary efficacy endpoint for Part II is the composite image quality score defined in 18.4.1. Data will be tested for normality using the Shapiro-Wilk and Shapiro-Francia tests. The composite subjective image quality score will be compared between ventilator-gated MUSIC-MRI and the self-gated MUSIC-MRI using a paired t-test with appropriate transformation if needed. If the data are not normally distributed and transformation is not possible, a Wilcoxon-sign-rank test will be considered. The null hypothesis is that the mean difference in the image quality scores of the self-gated images is smaller than or equal to the mean from ventilator-gated images with the non-inferiority margin of -1.75 (self-ventilator ≤ -1.75). The alternative hypothesis is that the mean difference in image quality score of self-gated images from the ventilator-gated images is greater than the non-inferiority margin of -1.75 (self-ventilator > -1.75) (see the detail of choosing the margin in section 18.7.2.).

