18.5 Secondary Efficacy Endpoints

18.5.1 Part I – Differences in individual image quality score (per segment or structure), image sharpness values, and CNR measurements for Feraheme vs Ablavar

The secondary efficacy endpoints for Part I are the individual image quality score for each of the seven anatomical structures as defined in 18.3, the image sharpness values for the ascending aorta and the interventricular septum, and the CNR measurements for each contrast agent. Data will be tested for normality using the Shapiro-Wilk and Shapiro-Francia tests. The average image quality scores of each anatomic structure between two readers, the image sharpness values, and the CNR measurements will be compared using a parametric two group t-test with an appropriate transformation if needed. If the data are not normally distributed and transformation is not possible, a non-parametric Wilcoxon-rank-sum test will be considered. Kappa statistics will be reported between two independent scores in each secondary endpoint.

18.5.2 Part II – Differences in individual image quality score (per segment or structure), image sharpness values, and CNR measurements for ventilator-gated vs self-gated MUSIC-MRI

The secondary efficacy points for Part II are the individual subjective image quality score for each of the seven anatomical structures as defined in 18.3, the image sharpness values for the ascending aorta and the interventricular septum, and the CNR measurements for the two MRI techniques. Data will be tested for normality using the Shapiro-Wilk and Shapiro-Francia tests. The average image quality scores of each anatomic structure between two readers, the image sharpness values, and the CNR measurements will be compared using a paired t-test with the margin of non-

inferiority of 0.75 for the image quality scores. If the data are not normally distributed and transformation is not possible, a non-parametric Wilcoxon-rank-sum test will be considered. Kappa statistics will be reported between two independent scores in each secondary endpoint.

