score. The margin of 1.75 was derived using an expected mean of 24.75 for the self-gated image (~4% reduction in image quality score compared to that achieved with the ventilator-gated method). The non-inferiority comparison will be a one-sided test at a 0.025 level of statistical significance and a -1.75 margin. A sample size of 36 will achieve a statistical power of greater than 90% to detect non-inferiority between ventilator-gated and self-gated MUSIC-MRI using a one-sided t-test with a non-inferiority margin of -1.75 and a true difference of zero with a standard deviation of 3.0 and a significance level of 2.5%. Taking into account missing data due to unusable image quality or incomplete studies, we plan to enroll 40 CHD subjects.

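### Part II: the seven structure margins of 0.75 add up to 5.25, three times the 1.75 allowed on their sum, with no rationale and no link to the primary test

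*Combined protocol and SAP*

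**What the plan says.** Section 18.4.1 defines the composite as the "sum of the subject image quality scores assigned to seven important anatomical structures for pediatric CHD patients". Section 18.3 scores each structure from 1 to 4, so the composite runs from 7 to 28. Section 18.4.2 carries this into Part II: "The primary efficacy endpoint for Part II is the composite image quality score defined in 18.4.1". The alternative hypothesis there is a mean difference "greater than the non-inferiority margin of -1.75 (self-ventilator > -1.75"), and section 18.7.2 fixes the test: "The non-inferiority comparison will be a one-sided test at a 0.025 level of statistical significance and a -1.75 margin".

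The first Part II secondary endpoint in section 8.2.2 is "Statistically non-inferior image quality scores for the self-gated MUSIC-MRI in each of the 7 important anatomical structures". Section 18.5.2 tests these scores by paired t-test with a limit of non-"inferiority of 0.75 for the image quality scores".

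Section 18.7.2 offers a derivation for 1.75, from an expected self-gated mean of 24.75 against 25.62 for ventilator gating. No section explains 0.75, gives a significance level for the structure tests, or makes them conditional on the primary result.

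**The concern.** Because the composite is an unweighted sum, the two margins can be compared directly. The primary tolerates an average loss of 0.25 per structure and the secondaries tolerate 0.75. A report could therefore state that self-gated imaging is non-inferior for each of the seven structures, while the test on their sum, in the same children, fails. A reader who saw seven favourable structure results could take them as support for a technique that had missed its own primary criterion.

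**Working it through.** **Reproducing the plan's figure.** Section 18.7.2 states power above 90% for 36 pairs, margin 1.75, SD 3.0 and true difference 0. With a one-sided paired t-test at 0.025 and 35 df, the noncentrality is 1.75 × √36 / 3.0 = 3.5 and power is 92.5%. The stated figure holds.

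**Comparing the margins.**
- Sum of structure margins: 7 × 0.75 = 5.25, and 5.25 / 1.75 = 3.0.
- Composite margin per structure: 1.75 / 7 = 0.25.
- Share of scale range: 0.75 / 3 = 25% per structure; 1.75 / 21 = 8.3% for the composite.
- Loss the plan expects: 25.62 − 24.75 = 0.87, or 0.87 / 7 = 0.12 per structure.

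**Can the two results conflict at n = 36?** The documents give no per-structure SD or correlation. Assumptions: equal structure SDs s, a common correlation ρ, the same true loss in every structure, and one-sided 0.025 for the structure tests. To keep the composite SD at 3.0, 7s² + 42ρs² = 9, so s = 3 / √(7 + 42ρ).

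A structure passes if its observed loss is below 0.75 − 2.030 × s / 6, where 2.030 is the t critical value. The composite's 95% interval has half-width 2.030 × 3 / 6 = 1.015, so it lies wholly below −1.75 only if the observed composite loss exceeds 1.75 + 1.015 = 2.765. Simulation with 10,000 trials per cell gave:

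| | ρ = 0 | 0.3 | 0.5 | 0.8 | 1.0 |
|---|---|---|---|---|---|
| Structure SD s | 1.13 | 0.68 | 0.57 | 0.47 | 0.43 |
| Largest equal observed loss passing | 0.37 | 0.52 | 0.56 | 0.59 | 0.60 |
| True loss 0.30 (composite 2.1): all seven pass | 4–5% | 85% | 98% | ~100% | ~100% |
| … and whole composite interval below −1.75 | 0% | 3% | 8% | 10% | 10% |
| True loss 0.40 (composite 2.8): all seven pass | 0.3% | 45% | 79% | 97% | ~100% |
| … and whole composite interval below −1.75 | 0% | 11% | 34% | 50% | 53% |
| True loss 0.50 (composite 3.5): all seven pass | 0% | 10% | 34% | 71% | 92% |
| … and whole composite interval below −1.75 | 0% | 5% | 26% | 64% | 85% |

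The composite test passes in 0.4% of trials at loss 0.30 (noncentrality (1.75 − 2.1) × 6 / 3 = −0.7) and in essentially none at 0.40 or 0.50. As a check on the first column, a single structure with SD 1.13 and true loss 0.30 passes with probability 0.639, and 0.639⁷ = 0.043.

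**Would 0.25 work as a margin?** At zero true difference and n = 36, power per structure against 0.25 is 25%, 58%, 73%, 87% and 92.5% across the five correlations. Against 0.75 it runs from 97% to about 100%.

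**The case against.** The structure scores are secondary endpoints in a study that calls itself exploratory. No rule lets them rescue or override the primary test. A component margin need not equal the composite margin divided by seven: a two-reader average on a four-point scale is coarse, and 0.25 could leave too little power. All of this stands. It means a margin wider than 0.25 could be defended, but the plan does not argue for one.

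Three stronger readings are tempting, and the documents do not support them.

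- *A reader might infer that self-gated images could readily pass on all seven structures while clearly inferior overall.* Failing a non-inferiority test does not demonstrate inferiority. At a loss of 0.30, all seven passing with the whole composite interval below −1.75 occurs in about 0–10% of trials. It becomes common only at larger losses with correlated structures, and is practically unreachable at zero correlation.
- *A reader might infer that a total loss near 5.25 would pass.* That figure bounds the true loss. An equal observed loss must stay below about 0.37–0.60 per structure, or 2.6–4.2 in total.
- *A reader might subtract 0.75 from the average of 25.62 / 7 = 3.66, get 2.91, and conclude that passing structures fall below a diagnostic level.* From 3.66, the passing limits leave an observed mean of about 3.05–3.29. The even split across structures is itself an assumption, and section 18.3 labels only score 1 as nondiagnostic.

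**Conclusion.** The structure margins are inconsistent with the primary margin by an exact factor of three, without explanation or gating. Under the stated assumptions, the practical result is that all seven structures could be called non-inferior in 85–98% of trials at correlation 0.3–0.5 when the true composite loss already exceeds the primary margin and the primary almost never passes. At zero correlation that falls to about 4–5%. Positive correlation is plausible, since the scores share one acquisition, one gating method and the same readers, but the documents do not quantify it. The consequence is contradictory secondary statements. The primary test is not in error, and its sample size reproduces.

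**What to change.** In sections 8.2.2 and 18.5.2:

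1. Remove 0.75 as a pass/fail rule for the structure scores.
2. Report each structure's mean paired difference (self-gated minus ventilator-gated) with its 95% confidence interval. Show −0.25 (1.75 / 7) as a reference line only. Making it a decision threshold would be a separate trade-off, given power of 25–92.5% at zero difference.
3. Tabulate, by technique, the number of children scored below 3 for each structure. This is descriptive, and shows where detail is lost; for the coronary arteries, for example, the next level down is "2=only origins of main coronary arteries confidently identifiable".
4. State that structure-level results do not support a non-inferiority claim when the composite test fails.

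The cost is some rewording and one table. The structure endpoints become estimates and no longer earn a formal non-inferior label. The primary analysis and the planned 40 children are unaffected.

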18.6 Safety Evaluations

AEs, SAEs, AEs resulting in premature withdrawal from the study, AEs of special interest (hypersensitivity reactions and blood pressure changes requiring intervention), and study related adverse events will be listed and summarized by contrast agent group. For the purpose of safety evaluation, the patients in both Part I and Part II who received the same contrast agent will be included in a single safety report. Due to the limited study cohort size and the small anticipated AE rates, no formal inferential statistical analyses will be performed for AEs. However, while the study is too small to expect statistical significance in sub-groups, the efficacy and safety results will be examined by standard age categories (neonates (0-to-1 month of age), infants and toddlers (1 month to 2 years of age) and children (>2 years of age)) and any clinically important differences reported.

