6 STUDY OBJECTIVES

1. To compare the diagnostic efficacy of Ablavar®-based MUSIC-MRI with Feraheme®-based MUSIC-MRI in pediatric patients with CHD. (Study Part I)
2. To determine the diagnostic efficacy of an accelerated self-gated MUSIC-MRI cardiovascular MRI technique for pediatric patients with CHD, which ultimately may not require sedation or general anesthesia. (Study Part II)
3. To summarize the safety of Feraheme® and Ablavar® as an MRI contrast agent in pediatric patients with CHD.

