9 SUBJECT SELECTION

9.1 Study Population

Pediatric patients of all ethnicities, age newborn to 6 years, of either gender with known or suspected CHD will be recruited. This specific age population has been chosen because our preliminary experiences suggest that the PDB is greatest in the smallest and sickest children. Furthermore, all patients of ages < 6 years undergoing cardiac MR imaging are routinely examined under anesthesia with controlled ventilation independently of our study and under the direct and

continuous observation of a pediatric anesthesiologist or neonatologist. These elements minimize the relative risk of Feraheme® administration by enabling airway protection and the ability to perform non-breath-held diagnostic studies in potentially fragile patients. Our study population will include patients with any types of CHD who are clinically referred to cardiovascular MRI; however, we expect our patient recruitment to be concentrated in more complex forms of CHD, such as Tetralogy of Fallot, because these are the patients that typically have inadequate echocardiographic exams and are referred for MRI. We do not expect our study population to have eGFR<40 mL/min/1.73m², although renal insufficiency is an exclusion criteria for the Ablavar® group of Part I study.

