9.3 Exclusion Criteria

1. Standard clinical contraindication to MRI, including subjects with cochlear implants and implanted cardiac devices
2. Subjects with past or current diagnosis of iron overload due to hereditary hemochromatosis or other causes (for subjects receiving Feraheme® injection only).
3. Subjects with known hypersensitivity or allergy to iron oxide particles.
4. Subjects with renal insufficiency defined as estimated glomerular filtration rate (eGFR) < 40 mL/min/1.73m² (for subjects receiving Ablavar® injection only).
5. Subjects who are critically ill at the time of MRI and for whom the period of general anesthesia and separation from the critical care nursery or intensive care unit poses added risk as deemed by referring cardiologists, cardiac surgeons or the managing radiologist (for Part II only).
6. Other medical conditions, in the judgment of the clinician investigator, that would increase the risks to the child related to participation in the study.

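### Section 18.6 pools Part I and Part II safety by contrast agent although exclusion 5 applies to Part II only, so under stated conditions the agent carried forward is expected to show a lower AE rate with no drug difference

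*Combined protocol and SAP*

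**What the plan says.** Objective 3 (Section 6) is "To summarize the safety of Feraheme® and Ablavar® as an MRI contrast agent in pediatric patients with CHD". Section 18.6 carries it out. AEs, SAEs, AEs of special interest and related events "will be listed and summarized by contrast agent group", and "the patients in both Part I and Part II who received the same contrast agent will be included in a single safety report". The only further breakdown is by age category. The analysis is descriptive: "no formal inferential statistical analyses will be performed for AEs".

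Exclusion 5 in Section 9.3, repeated in the Synopsis, covers "Subjects who are critically ill at the time of MRI and for whom the period of general anesthesia and separation from the critical care nursery". The criterion names the ICU as well, and it needs a clinician's view that the procedure "poses added risk as deemed by referring cardiologists, cardiac surgeons or the managing radiologist (for Part II only". Part I has no such exclusion. Section 9.1 explains the choice of age range by saying that "our preliminary experiences suggest that the PDB is greatest in the smallest and sickest children".

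Other relevant places:

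- Sections 7.2 and 7.3: one agent is carried into Part II, and all 40 Part II children receive it.
- Section 7.3: apart from the added imaging sequence and the enrollment target, Part II is described as having the same design as Part I. Exclusion 5 is not mentioned there.
- Sections 8.1.3 and 8.2.3: safety endpoints are listed separately for each part.
- Section 18.2: demographics are summarized by treatment group and study part.
- Sections 14.1 and 12.1: AEs are counted whatever their cause, with a record review at 60 days.
- Section 14.2: SAE collection ends once the study-visit procedures are complete.

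**The concern.** The by-agent safety columns will not be built from comparable children. One column holds a Part I group only. The other holds a Part I group plus about 40 children screened under a stricter rule. AEs are all-cause, and review runs to 60 days in children with congenital heart disease, so underlying illness can contribute to the counts. Blood pressure changes requiring intervention, an AE of special interest, could also reflect baseline illness during the procedure itself.

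Any difference between the columns would then mix the drugs with the change in eligibility. The direction is tied to the image-quality result, because the agent that does better in Part I normally gains the Part II children. A reader of the final report would have no per-part table from which to separate the two.

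**Working it through.** **Inputs from the documents.** Part I has 40 per agent (18.7.1). The interim analysis is at about 20 per agent and may close Part I (7.2, 18.4.1). Part II has 40 children on one agent (7.3, 18.7.2).

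The plan states no figure for the safety comparison, but the sizes that set the pooling weights can be reproduced. With a difference of 1.75, SD 2.10 and two-sided alpha 0.025, the normal approximation gives n = 36 per group (power 90.2%; exact t-test 89.1%). Allowing for 10% unusable images, 36/0.90 = 40. At n = 20 the exact t-test gives 62.0%, matching the stated 62%. On the design's own assumptions, early closure is therefore a likely outcome.

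**Inputs not in the documents (assumed).** q is the share of Part I children who would meet exclusion 5. rc is the AE rate in those children and rn the rate in all others. The drugs are equal, q is the same in both Part I groups, and Part II contains none of these children.

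**Formulas.** With n1 per group in Part I and n2 = 40 in Part II:

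- Other agent: q·rc + (1−q)·rn = rn + q(rc−rn)
- Carried agent: [n1(rn + q(rc−rn)) + n2·rn]/(n1+n2) = rn + [n1/(n1+n2)]·q(rc−rn)
- Expected gap: [n2/(n1+n2)]·q(rc−rn)

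At full Part I the weight is 40/80 = 1/2. After early closure it is 40/60 = 2/3.

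**Results.**

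| q | rn | rc | Other agent | Carried, 40+40 | Gap (points) | Carried, 20+40 | Gap (points) |
|---|---|---|---|---|---|---|---|
| 10% | 5% | 10% | 5.5% | 5.25% | 0.25 | 5.17% | 0.33 |
| 30% | 10% | 30% | 16.0% | 13.0% | 3.0 | 12.0% | 4.0 |
| 50% | 10% | 40% | 25.0% | 17.5% | 7.5 | 15.0% | 10.0 |

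If rc = rn or q = 0, the gap is zero.

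**Chance.** Exact binomial calculation gives the probability that the carried agent's observed rate is the lower one. Over these scenarios it runs from 0.45 to 0.80 (80 vs 40) and from 0.43 to 0.80 (60 vs 20). In the middle row at 80 vs 40 it is 0.63 lower, 0.07 tied and 0.31 higher (rounded). With no difference in rates (rc = rn = 10%) the same layout gives 0.45 lower and 0.47 higher.

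**Unequal Part I case mix.** Let the Part I shares be qc (carried agent) and qo (other agent). The expected advantage vanishes when [n1/(n1+n2)]·qc = qo. That is qc = 2·qo at full Part I and qc = 3·qo after early closure. Beyond that it reverses.

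**After the fix.** Comparing 40 vs 40 (or 20 vs 20) within Part I, the expected gap from the eligibility change is zero for any q, rc and rn, given the same case mix in both groups.

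**The case against.** The strongest reply is that the plan makes no formal safety comparison between agents. Objective 3 asks for a summary, AEs are descriptive, and Section 18.1 says that results are reported separately by agent. This limits the consequence, since no test is biased. It does not remove the point: a summary by agent group gives two figures that will be read against each other, and the absence of inference does nothing about the mix of children.

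Second, Section 8.1.3 already names AE incidence in the Part I test and control groups as an endpoint, and Section 8.2.3 lists Part II safety separately. That is correct and shows the intent. But Section 18.6 governs the final safety report and does not call for those per-part tables.

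Third, if Part I is not significant, the DMC is asked to weigh safety differences seen in Part I (Section 7.3). That advice precedes Part II, so pooling cannot affect it. This stands in full.

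Fourth, the eligibility contrast is narrower than it first appears. Exclusion 5 needs both critical illness and a clinician's judgment of added risk. The Part II study flow in the Synopsis still includes intubated transfers from the neonatal ICU. Exclusion 6 applies to both parts and may remove some of the same children from Part I. All this stands and could make q small. A reader might infer that Part II contains no critically ill children; the documents do not support that.

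Fifth, parents choose the agent in Part I (Section 11.1.1), and the iron-overload and eGFR exclusions depend on the agent. Equal Part I case mix is therefore an assumption. This stands, and Part I-only tables would remain open to confounding.

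Sixth, Section 18.6 anticipates small AE rates, which favors the lower end of the range. This also stands.

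**Conclusion.** The point holds as a defect in how safety is tabulated. Pooling by agent, an exclusion confined to Part II, and one agent carried forward together put a change in eligibility into the by-agent safety columns. Section 18.6 offers no per-part layout to expose it.

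The expected gap favors the carried agent by q(rc−rn)/2 at full Part I, or two thirds of q(rc−rn) after early closure. It requires that children meeting exclusion 5 have more AEs, that some of them enter Part I, and that the Part I groups are alike. None of q, rc and rn is given. The assumed ranges yield about 0.3 to 10 points.

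A reader might infer that the carried agent is bound to look safer. The documents do not support that: the gap may be well under 1 point, chance can reverse it at these sizes, and non-randomized choice of agent can offset it. A reader might also extend the 60-day argument to SAEs. On the wording of Section 14.2, SAE collection ends after the visit procedures, so the argument covers AEs. Confidence is high in the structure and moderate in direction and size.

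**What to change.** In Section 18.6:

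- Tabulate AEs, SAEs and AEs of special interest by agent and by study part, in line with Sections 8.1.3, 8.2.3 and 18.2.
- State that any reading of Feraheme against Ablavar rests on Part I only, and that Part I is non-randomized and may be confounded.
- Show the pooled Part I and Part II figure only as a single-agent exposure summary, beside the per-part figures.

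The statement in Section 7.3 that Part II otherwise matches Part I should be reconciled with the Part II-only exclusion in Section 9.3.

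The cost is a sentence or two and extra table columns, with no new data. The downside is smaller denominators: the between-agent view rests on 40 vs 40, or 20 vs 20 after early closure.
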